10.3 Data Analyses Plans

A formal statistical and analytical plan (SAP) including additional statistical analysis details will be completed prior to database lock.

10.3.1 Analysis Datasets

All the analysis will be conducted in the safety population, including all the patients who received at least one dose of NSC-CRAd-S-pk7.

10.3.2 Description of Statistical Methods

10.3.2.1 General Approach

All study data will be presented in by-subject data listings. Statistical analysis will be descriptive only, with no hypothesis testing. All the endpoint data will be collected and described in summary tables for both two arms at each dose. In general, descriptive statistics (n, mean, standard deviation, median, minimum, and maximum) will be presented for continuous variables. Frequencies and percentages will be calculated for categorical and ordinal variables at each category. Statistical analyses will be performed using SAS9.4 (SAS Institute Inc., Cary, NC)

10.3.2.2 Analysis of the Primary Endpoint(S)

The maximum tolerated dose (MTD) will be determined according to the dose escalation algorithm described in Section 4.2. Dose limiting toxicities are defined in Section 4.2.1. If >2 patients do not complete the initial RT/TMZ phase or rule if > 2 patients experience life threatening or fatal neurologic toxicity, the trial will be stopped to analyze, in conjunction with the DMC, whether this regimen is tolerable.

10.3.2.3 Analysis of the Secondary Endpoint(S)

For objective tumor response, a summary table will be produced to present the number and proportion of responders in each arm, together with each of the response categories, namely CR, PR, MR, SD, P and PP.

The analysis of overall survival and progression-free survival are based on the survival function, estimated by the Kaplan-Meier method. Survival will be calculated from the day of study inclusion until progression and death, respectively, or will be censored at the date of last available follow-up information. The survival function will be summarized for 25th percentile, median, and 75th percentile, and the survival curves of the two arms will be presented.

Descriptive statistics will be used to describe the overall quality-of-life score on physical well-being, social/family well-being, emotional well-being, functional well-being and additional concerns, respectively.

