4.8 Duration of Therapy

Within 28 days of screening, patients will receive a one-time intratumoral injection of NSC-CRAd-S-pk7 during the resection or biopsy procedure, at the dose specified in the dose-escalation protocol. Patients will remain inpatient for standard of care post-operative procedures, including an MRI of the brain. Discharge will take place when clinically appropriate.

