5.0 STUDY PROCEDURES

All patients will undergo all standard of care and clinically indicated evaluations in addition to any study specific evaluations. **Table 3** presents a summary sample schedule. **Table 4** outlines the treatment evaluation schedule. **Table 5** presents the entire study calendar.

Table 3– Sample Schedule	
Screening	
Day -28 until Day -1	Informed consent, medical history and physical exam. baseline laboratory assessments, MRI
Week 1	
Day 0	Intratumoral injection of NSC-CRAd-S-pk7
Days 6-7 (+ 3days)	Simulation for RT
Week 2-7	
Days 1-7 (+ 3days)	RT (1.8-2 Gy) (Days 1-5 only) TMZ (75 mg/m ²)
Week 12	
5 Days on/23 Days off	TMZ (150-200mg/m ²)

Table 4 – Treatment Evaluation Schedule	
History, Physical Exam	≤ 7 Days from Day 0 Weekly 2-4 weeks after completion of XRT At least every three months for first year Annually for five years
Quality of Life questionnaire (FACT-Br version 4) and mini-mental status exam	≤ 7 Days from Day 0 Once during RT administration (week 2 or 3) 2-4 weeks after completion of RT Every three months for the first year or until disease progression
CBC, platelets, PT, PTT, serum electrolytes, creatinine, liver function tests-AST, ALT and bilirubin	≤ 7 Days from Day 0 Weekly during administration (weeks 2, 4, and 6) Annually for five years (CBC Count)
Blood collection for immune research studies*	≤ 7 Days from Day 0 (may be collected in week 2-3 after the NSC-CRAd injection and 2-4 weeks after completion of RT)
Blood collection for RCR testing*	≤ 7 Days from Day 0, 3 months, 6 month, and one year, then annually
Urine/serum pregnancy test (if applicable)	≤ 7 Days from Day 0
Brain MRI	≤ 21 Days from Day 0 2-4 weeks after completion of RT

	Every two-three months for the first year or until disease progression Annually for five years
--	---

Table 5. Activities	Screening	Study Drug Administration Period							Follow-up Period			
	Day -28 to -1	Day 0	Day 1	Day 2	Day 3	Day 7	Day 14	Day 28	Day 42	Day 56, every 8 weeks thereafter	Yearly	
Clinical Assessments												
Informed Consent	X											
Medical/Cancer History	X											
Physical Exam /targeted neurological exam	X	X	X	X	X	X	X	X		X		X
KPS	X	X						X	X		X	X
Height (only at Screen) and Weight	X					X	X	X				
Vital Signs	X	X	X	X	X	X	X	X				
Adverse Events	X	X	X	X	X	X	X	X		X		
Concomitant Meds	X	X	X	X	X	X	X	X			X	
Quality of Life Measures	X						X				X ³	
Clinical Laboratory												
Urine or serum Pregnancy test	X	X										

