6.2 Secondary Endpoints

This phase 1 study is not powered to detect statistically significant differences in efficacy.

However, data will be collected and described descriptively on the following endpoints:

- objective tumor response: objective response to therapy as determined by iRANO criteria (table 9)
- overall survival : time from study project injection to death
- progression-free survival : time from study project injection to first confirmed disease progression as determined by objective tumor response
- quality of life: summary score on patient self-report measure, Functional Assessment of Cancer Therapy- Brain component (as determined by patient self-report on FACT-Br v4, appendix C)

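### OS and PFS start at injection in Section 6.2 but at an undefined study-inclusion date in Section 10.3.2.3, which can add about 0 to 28 event-free days to a patient's time

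*Combined protocol and SAP*

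**What the plan says.** Section 6.2 (Secondary Endpoints) defines OS as "time from study project injection to death" and PFS as "time from study project injection to first confirmed disease progression as determined by objective tumor response". The word project is evidently a slip for product, so both clocks start on Day 0.

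Section 10.3.2.3 (Analysis of the Secondary Endpoint(S)) gives the rule that will be programmed for the Kaplan-Meier curves, median and quartiles: "Survival will be calculated from the day of study inclusion until progression and death, respectively". The plan does not say what date inclusion is.

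Section 10.3.1 (Analysis Datasets) sets the population: "All the analysis will be conducted in the safety population, including all the patients who received at least one dose of NSC-CRAd-S-pk7".

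On timing, Table 3 in Section 5.0 places consent and baseline work at "Day -28 until Day -1", and Table 5 marks both consent and registration under Screening. Section 4.8 says "Within 28 days of screening, patients will receive a one-time intratumoral injection of NSC-CRAd-S-pk7". Section 3.0 does not allow treatment before registration.

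**The concern.** The two sections give two sets of survival times from the same data, and nothing elsewhere says which one governs.

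The conflict also has a direction. The clock in Section 10.3.2.3 may start before injection, while the population in Section 10.3.1 is selected at injection. A patient who dies or drops out between inclusion and injection never enters the analysis, and no post-baseline tumour assessment is scheduled before Day 0. Any time between the two dates is therefore immortal time: it can lengthen a patient's OS or PFS but cannot shorten it, and enrolling more patients does not remove it.

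At stake are the descriptive OS and PFS summaries, which are shown as one curve per arm. The waiting time for biopsy (Arm A) and for resection (Arm B) could differ, and such a difference would appear as part of any gap between the two curves. The exploratory Cox model in Section 10.3.2.4 uses the same OS variable.

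**Working it through.** The plan states no expected median, event count or power for OS or PFS, so there is no survival figure of its own to reproduce. The check bounds the lag and then its effect.

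**1. The lag.** For patient i, lag(i) = injection date − inclusion date.
- If inclusion is consent or registration in the screening window (Tables 3 and 5), the minimum is 0 − (−1) = 1 day and the maximum is 0 − (−28) = 28 days. Section 4.8 gives the same maximum.
- If inclusion is registration and registration waits for surgical pathology, the lag is about 0. Section 11.3.1 asks for a pathology report before registration, and Section 3.1.1 has the diagnosis confirmed on frozen section at surgery.

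The documents therefore support about 0 to 28 days, varying by patient.

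**2. Effect on each time.** Every analysed patient was injected, so

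T(from inclusion) = T(from injection) + lag(i), with lag(i) ≥ 0.

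Censoring dates are fixed in the calendar, so censored times lengthen in the same way.

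**3. Effect on the Kaplan-Meier percentiles.** With a common lag, the whole curve moves right by that lag. With unequal lags and complete follow-up, each percentile moves right by an amount between the smallest and the largest lag. If lags are unequal and some patients are censored, events and censorings can change order, and in a small arm that bound is then approximate. The individual times still only lengthen.

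**4. Size.** One month is taken as 30.44 days. The medians of 10, 12 and 15 months come from Section 1.1 and serve only as a scale.
- 28 days: 28 / 30.44 = 0.92 months.

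| Median from injection | With a 28-day lag | Increase |
|---|---|---|
| 10 months | 10.9 months | 0.92/10 = 9.2% |
| 12 months | 12.9 months | 0.92/12 = 7.7% |
| 15 months | 15.9 months | 0.92/15 = 6.1% |

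- 14 days: 14 / 30.44 = 0.46 months, and 0.46/15 = 3.1%.
- 12-month survival with a 15-month median, assuming an exponential curve: 2^(−12/15) = 57.4%. With a 28-day lag it is 2^(−(12 − 0.92)/15) = 59.9%.
- PFS: the documents give no median. Assuming 5 to 7 months, a 28-day lag adds 0.92/7 = 13% to 0.92/5 = 18%.

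**5. A less extreme case.** A simulation used 18 patients per arm, exponential survival, no censoring and lags uniform on 1 to 28 days; the last three are assumptions. The median moved by 14.6 days on average. In single simulated trials the shift ranged from 1 to 28 days, so it need not equal the average lag.

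**6. Cox model.** The partial likelihood depends on the order of event times and on who is at risk at each. A common lag changes neither, so the hazard ratio stays the same. Unequal lags matter only if they reorder times or alter risk sets. The documents do not allow that effect to be sized.

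**The case against.** The best counter-argument concerns size and certainty. Study inclusion is undefined, and the pathology requirement in Section 11.3.1 may put registration at or near Day 0, where the conflict has almost no numerical effect. That reading is possible but not established: Table 5 shows registration under Screening, and Section 3.2.2 allows a prior biopsy, so a pathology report could exist well before surgery. The ambiguity widens the range down to zero but does not settle the origin.

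A reader might infer that every patient gains 28 days. The documents do not support that. Twenty-eight days is the edge of a window. Table 4 puts most baseline work within 7 days of Day 0 and the MRI within 21 days. Those windows do not date consent, but they give no reason to treat 28 days as typical. The 6.1% and 9.2% figures are therefore maxima.

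A reader might also infer that the Cox result is biased, or that the trial will look better against the 10- and 15-month medians. The first follows only under the condition in step 6. As to the second, the plan specifies no comparison with those medians, and the time origins behind them are not given.

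Finally, these summaries are descriptive, the study is not powered for efficacy, and Section 10.3 promises a formal SAP before database lock. All of that stands and limits the priority. It does not resolve the contradiction. The later document is meant to add detail, and in an open-label trial the time origin is better fixed before outcomes accumulate.

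**Conclusion.** The rule in Section 10.3.2.3 is wrong as written. It contradicts the endpoint definitions in Section 6.2 and, combined with an injected-only population, it can credit patients with time in which they could not have been counted as dying. Its effect on the Kaplan-Meier median and quartiles for OS and PFS is upward, by an amount between the smallest and largest lag when follow-up is complete. The supported range is about 0 to 28 days. The upper end assumes that inclusion falls at the very start of screening for everyone, and a 14-day lag is about 3% of a 15-month median. Where in the range the truth lies depends on a date that the plan does not define.

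The stronger inference, that the trial's main conclusions are at risk, is not supported. MTD determination, dose escalation and the safety analyses do not use this time origin.

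**What to change.** In Section 10.3.2.3, replace study inclusion as the starting point with the day of NSC-CRAd-S-pk7 injection (Day 0) for both OS and PFS. This matches Section 6.2 and the analysis population in Section 10.3.1. It also matches the follow-up visits in Section 4.9 and the post-treatment immune sampling in Section 9.0, which are already timed from injection.

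Correct the events in the same sentence. The section names OS and then PFS, but the sentence lists progression and then death, respectively, so read literally it pairs OS with progression and PFS with death. It should say OS until death and PFS until progression. While editing, the sponsor should also state how a death without progression is handled in PFS, because Section 6.2 does not name it as an event.

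The cost is one reworded sentence. It needs no new data and no change to patient care. Reported medians may become slightly shorter. If the sponsor prefers an inclusion origin, inclusion must be defined and all included patients analysed, which is a larger change.

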4.9 Duration of Follow Up

Patients will have a follow-up visits days 1-3 while hospitalized, days 7, 14, and 28 after NSC-CRAd-S-pk7 administration and then at day 56, and every 8 weeks after until disease progression or patient withdrawal. They will be monitored for toxicities by physical exam and laboratory results through day 56. They will also undergo a brain MRI on day 28 and at day 56 to monitor for toxicity and disease progression, then every 8 weeks to monitor for disease progression. Survival status will be monitored until patient death or for up to 5 years.

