Appendix A. iRANO criteria	
Term	Criteria
Complete Response (CR)	The enhancing tumor is no longer seen by neuroimaging, with the patient off all steroids, or on adrenal maintenance only.
Partial Response (PR)	Decrease of $\geq 50\%$ in the product of two diameters with the patient on a stable or decreasing dose of steroids, with a stable or improving neurologic examination for at least six weeks.
Minor Response (MR)	Decrease in diameter products of $< 50\%$ with the patient on a stable or decreasing dose of steroids, with a stable or improving neurologic examination for at least six weeks.
Stable Disease (SD)	The scan shows no change. Patients should be receiving stable or decreasing doses of steroids.
Progression (P)	Increase of $> 25\%$ in tumor area (two diameters) provided that the patient has not had his/her dose of steroids decreased since the last evaluation period. A concomitant decrease in steroid dose will rule out a progression designation during the first two months after completion of radiation
Pseudoprogression (PP)	Radiological changes without concomitant neurological changes. It is not unusual to see enhancement in the context of oncolytic viral therapies. If thought to be the case, serial MRI imaging is warranted.

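### No section counts death as a PFS event, so the plan applied as written reports time to progression, with deaths censored, under the name PFS

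*Combined protocol and SAP*

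**What the plan says.** Section 6.2 (Secondary Endpoints) gives the definitions:

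- PFS: "progression-free survival : time from study project injection to first confirmed disease progression as determined by objective tumor response".
- OS: "overall survival : time from study project injection to death".

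Section 10.3.2.3 (Analysis of the Secondary Endpoints) gives the analysis rule. It names the endpoints in the order OS, then PFS: "The analysis of overall survival and progression-free survival are based on the survival function, estimated by the Kaplan-Meier method". It sets a different origin: "Survival will be calculated from the day of study inclusion". It then runs time "until progression and death, respectively, or will be censored at the date of last available follow-up information".

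Appendix A, which lists the response criteria, defines progression by growth in tumor area, "provided that the patient has not had his/her dose of steroids decreased since the last evaluation period". Death is not among its categories.

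The study summary and section 2.2 name PFS without defining it. Section 10.3 says that a formal SAP with further detail will be completed before database lock. On follow-up, section 4.9 says: "Survival status will be monitored until patient death or for up to 5 years".

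**The concern.** PFS is ordinarily read as time alive without progression, so death ends it. Here the only PFS event in section 6.2 is a confirmed progression, and the analysis section sends everyone without the terminal event to censoring. A patient who dies first is then handled as though progression could still occur later, and Kaplan-Meier assumes that such censoring says nothing about prognosis.

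The plan's own rules leave room for such deaths. Progression must be confirmed. Appendix A withholds a progression call in some circumstances when steroids have been reduced, and it adds a pseudoprogression category that calls for serial imaging. After day 56, section 4.9 schedules MRI every 8 weeks, so a patient can die between scans. Section 7.0 provides for review of deaths within 56 days. None of this says how often it will happen.

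At stake is the meaning of a reported result. The study summary commits to PFS curves and median estimates with confidence limits, and a reader will take those as PFS.

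**Working it through.** **1. No plan figure to reproduce.** The documents state no PFS median, rate or event count.

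**2. Which event ends PFS?**

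| Source | OS ends at | PFS ends at |
|---|---|---|
| Section 6.2 | death | confirmed progression |
| Section 10.3.2.3, read literally | progression | death |
| Section 10.3.2.3, order repaired to match 6.2 | death | progression |

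The literal reading contradicts section 6.2 for both endpoints, so a transposition is the evident explanation. No row gives progression or death, whichever comes first.

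**3. What happens to a death without recorded progression?** It is not a PFS event in section 6.2 or in the repaired section 10.3.2.3, and Appendix A does not turn it into progression. The remaining rule is censoring at the last available follow-up. Because survival status is followed, that is the date of death.

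**4. Direction.** At such a death, with n patients at risk, counting it multiplies the Kaplan-Meier curve by (1 − 1/n); censoring it multiplies by 1. The patient leaves the risk set at the same moment either way, so all later factors are the same. The censored version is therefore never below the version that counts the death.

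**5. Size.** Assume constant hazards: total hazard λ for the first of progression or death, of which a share f is death without recorded progression.

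- Median with deaths counted: ln 2 / λ.
- Median with deaths censored: ln 2 / [(1 − f)λ].
- Ratio: 1/(1 − f).
- Reading of the censored curve at the true PFS median, where it should be 0.500: 0.5^(1 − f).

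The value of f is an assumption, so a range is shown. The last two columns come from 5,000 simulated trials per row with 18 patients (the maximum per arm in section 10.2) and complete follow-up.

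| f | 1/(1 − f) | Curve at true median | Simulated trials with longer median | Simulated trials with shorter median |
|---|---|---|---|---|
| 0 | 1.00 | 0.500 | not run | not run |
| 5% | 1/0.95 = 1.05 | 0.518 | 37% | 0% |
| 10% | 1/0.90 = 1.11 | 0.536 | 61% | 0% |
| 20% | 1/0.80 = 1.25 | 0.574 | 86% | 0% |
| 30% | 1/0.70 = 1.43 | 0.616 | 96% | 0% |

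With 9 patients the simulated ratios of typical medians were 1.06, 1.12, 1.26 and 1.43 for f = 5 to 30%, close to the formula. With 18 they were 1.07, 1.16, 1.34 and 1.54. The excess is a small-sample effect: with an even number of patients, taking the first time the curve reaches 0.5 puts the median with deaths counted at about 0.93 of its true value. The formula is the figure to use.

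**6. Scale against sampling error.** With 18 events under the same model, the standard error of the log median is about (0.5/√18)/(0.5 × ln 2) = 0.34. A 95% range is then a factor of about exp(1.96 × 0.34) = 1.95 either way.

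**The case against.** The strongest reply has four parts.

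- **The censoring of deaths is inferred.** This is correct: no sentence says that a patient who dies without progression is censored, and section 10.3.2.3 ends PFS at progression only once its order is repaired. The inference is nonetheless the only outcome of the stated rules that agrees with section 6.2. A reader might instead conclude that the plan means to end OS at progression and PFS at death. The documents do not support that, because section 6.2 ties OS to death and PFS to progression.
- **The formal SAP is still to come.** It could settle the matter before any analysis. But the definition in section 6.2 is complete as it stands and omits death, so this is text to correct rather than detail to add.
- **The endpoint carries little weight.** PFS is secondary, the analysis is descriptive, and the study is not powered for efficacy. OS is reported separately, deaths are listed and by-subject listings are planned, so a careful reader could recompute PFS. Sampling error at 18 patients exceeds the bias at every f shown. All of this stands and limits the importance of the point. It does not remove the mislabelling, and the bias runs in one direction, unlike sampling error.
- **The magnitude is assumed.** This also stands. Neither f nor a PFS median is in the documents, and the constant-hazard model fits clustered early deaths poorly.

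A reader might further infer that the two arms' curves will show a false difference. That requires f to differ between arms, for which there is no figure. The arms are also defined by resectability rather than randomised, and no test between them is planned.

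**Conclusion.** The point holds as an error in definition. Following section 6.2, and section 10.3.2.3 with its transposition repaired, yields time to progression with deaths censored, reported as PFS. Given censoring at the date of death, the direction is certain: the curve is too high or unchanged, never too low.

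The size is conditional. Under constant hazards the median is inflated by 5%, 11%, 25% and 43% at assumed f of 5, 10, 20 and 30%, and not at all if every patient who dies has a recorded progression first.

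It would be too strong to say that PFS will be materially overstated in this trial, since the documents do not show that such deaths will be common. Nor is the trial's main purpose affected: dose escalation, the MTD, the recommended phase II dose and the sample size do not use PFS.

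**What to change.** Amend sections 6.2 and 10.3.2.3 together, and carry the same text into the formal SAP:

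- **Origin.** Use one for both endpoints. Section 6.2 uses injection and section 10.3.2.3 uses study inclusion. If inclusion means consent or registration, both of which Table 5 places in days −28 to −1, the two can differ by up to 28 days.
- **PFS.** Time from that origin to first progression or death from any cause, whichever comes first. A death without recorded progression is an event on the date of death. Censor patients alive without progression at their last tumor assessment.
- **OS.** Time from the same origin to death from any cause. Censor patients alive at last follow-up.
- **The sentence with the transposed events.** Replace it with these rules. Simply deleting it would remove the only censoring rule the document has for OS and PFS.
- **Time to progression, if wanted.** Report it separately under that name, with death as a competing event.

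The cost is a few sentences. No new data are needed, because survival status is already followed until death or up to 5 years. The one downside is that reported PFS may be shorter. Making the change before outcome data are examined avoids a choice of definition after the fact.
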